Within some medical specialities, the number of specific POCUS examination performed have been used as an indicator for scanning competence in re-certification¹². However, little is known about the number of performed POCUS examinations needed to secure skills. In general practice, continuous medical education (CME) programs have been found to increase GPs knowledge and skills in other areas¹³, but as POCUS is just a smaller part of the clinical work in general practice, CME programs for GPs cannot be too time-consuming.

7 Specific objectives

The overarching aim of this study is to investigate whether a quality assurance program, tailored for GPs who use POCUS as part of their patient examination in general practice, can lead to maintained scanning competence 12 months after baseline.

Primary outcome 1 (P1): For GPs, participating in a POCUS quality assurance program, the ultrasound competence score (summarized OSAUS score across ten scanning modalities), 12 months after baseline.

Primary outcome 2 (P2): The proportion of GPs, participating in a POCUS quality assurance program, with an ultrasound competence score (summarized OSAUS score across ten scanning modalities) at 12 months larger than or equal to the ultrasound competence score at baseline.

Secondary outcome 1 (S1): For GPs, participating in a POCUS quality assurance program, the OSAUS scores and the item scores, 12 months after baseline, for each of the ten scanning modalities included in the curriculum.

Secondary outcome 2 (S2): The proportion of GPs, participating in a POCUS quality assurance program, who have an ultrasound competence score (OSAUS score) of three or above, 12 months after baseline, for all of the seven OSAUS items of each of the ten scanning modalities included in the curriculum.

Secondary outcome 3 (S3): The proportion of GPs, participating in a POCUS quality assurance program, who rate themselves to be competent to perform un-supervised POCUS in general practice, 12 months after baseline, for each of the ten scanning modalities included in the curriculum.

Secondary outcome 4 (S4): The number of performed POCUS examinations by each GP each month during the study (months 1-12 after baseline).

Secondary outcome 5 (S5): The proportion of GPs, participating in a POCUS quality assurance program, who complete the online quiz at months 3, 6, 9 and 12 after baseline.

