This study will be conducted in office-based general practice in Denmark. GPs in Denmark are self-employed and work in office-based general practice clinics. Denmark has a public health care system where almost all patients are listed with a GP for primary health care. Consultations and treatments are free-of-charge for patients. GPs act as gatekeepers for other primary care healthcare providers and secondary care specialists. GPs are paid through a combination of remuneration and fee-for-service financed through taxes⁸. There is no fee for performing POCUS in primary care and GPs must cover expenses for the ultrasound device and their ultrasound education themselves. However, during this study participating GPs will have a fee for performing POCUS examinations. POCUS scanning-fees will be registered in the medical record system in the practice.

The study will be coordinated from CAM AAU and data will be collected by the research team and by the participating general practitioners in their clinics. All study data will be stored at a secure server at Aalborg University.

10 Participants

Eighteen GPs working in office-based general practice in Denmark, who have attended the PLOe ultrasound course¹⁰, will be invited to participate in the study. To participate a GPs must fulfill the inclusion criteria and not the exclusion criteria

Inclusion criteria:

1. GP, i.e., be a postgraduate medical doctor with a specialization in general practice.

- 2. Work in office-based general practice in Denmark
- 3. Have access to an ultrasound device in the practice during the study period

Exclusion criteria:

- 1. GPs with a possible conflict of interest (e.g., industry affiliation related to the use of ultrasound)
- 2. No signed informed consent to participate.

The quality assurance program will be developed and delivered by research team, who are experienced GPs, POCUS users and/or teachers. The competence assessment (OSAUS score) will be delivered by a team of POCUS experts (SKA, OG, MBJ, CS and LP), who have extensive POCUS experience.

11a Description of the intervention

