The research team has developed a Quality Assurance program as a CME-model for POCUS-using GPs. The program consists of an online quiz using a multiple choice questionnaire (MCQ) design. The participants are expected to complete the online MCQ at 3, 6, 9, and 12 months following baseline. The MCQ includes still-pictures and video sequences of the 10 application specific POCUS examinations from the course curriculum. Through 15-20 questions, the quiz tests participants (1) knowledge about indications for performing POCUS examinations, (2) applied knowledge of ultrasound equipment, (3) ability to optimize images, (4) ability to recognize and present structures, (5) ability to interpret images, (6) ability to describe and document findings and (7) medical decision-making. Each question has four possible answers of which up to three answers are correct. Each MCQ will have ten questions pertaining to pathologies within the ten applications of the curriculum. Further, there will be five to ten questions relating to image recognition, image optimisation, ultrasound artifacts. In each MCQ one or two of the questions will test the GP's knowledge in less frequent findings. We will predefine each included question in the MCQ according to: (1) scanning modality, (2) OSAUS dimension.

Once each MCQ is finalized, the participating GP's will receive feed-back on the answers with suggestions for improvement and guidance toward continuing self-directed learning. The MCQ part of the intervention is meant to function as a system of continuing medical education (CME).

11b Criteria for discontinuing or modifying allocated interventions for a given trial participant

The trial may be discontinued for a GP in case of withdrawal of an informed consent. Hence, data collection will stop for that person at the time of withdrawal of the informed consent. Otherwise, this is an intention-to-treat study hence participants will not be excluded because of low adherence to the educational elements. However, we will collect data of the degree of participation for each participant.

11c Strategies to improve adherence to intervention protocols, and any procedures for monitoring adherence

CAA will monitor participants' scanning activity and responses to the quizzes and reach out to participants, who fail be active or fail to complete the quizzes.

11d Relevant concomitant care and interventions that are permitted or prohibited during the trial

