During the assessment, only the participant and the assessor are present. Each assessment will follow the same structure, where experts will assess the participants by asking the following questions:

- In which clinical scenarios would you perform this POCUS examination (Item 1 in the OSAUS)

The experts will ask participants to demonstrate the POCUS examination (for maximum five minutes) to assess the following:

- Applied knowledge of the ultrasound equipment (Item 2 in the OSAUS)
- Image optimization (Item 3 in the OSAUS)
- Systematic examination (Item 4 in the OSAUS)
- Interpretation of images (Item 5 in the OSAUS)

The experts will present the participants with a picture of common pathology and ask the participants the following questions:

- How would you interpret these ultrasound findings? (Item 5 in the OSAUS)
- If you were to describe this examination in the medical record, what would you write? (Item 6 in the OSAUS)
- What would you do if you found it? (Item 7 in the OSAUS)

Following the assessment, the participant will receive feedback on the level of performance and educational advice. The total duration of the assessment is expected to last 90 minutes for each participant. The assessor completes an OSAUS score for each of the ten examinations performed by the participant.

The OSAUS assessment tool measures competency according to seven key domains: 1) Indication for the examination 2) Applied knowledge of ultrasound equipment 3) Image optimization 4) Systematic examination 5) Interpretation of images 6) Documentation of examination and 7) Medical decision making. Each domain is rated using a five-point Likert scale with descriptions of performance ranging from very poor (score=1) to excellent (score=5).

Figure 3. The OSAUS competence assessment tool

1. Indication for the examination	1	2	3	4	5
If applicable. Reviewing patient history and knowing why the examination is indicated.	Displays poor knowledge of the indication for the examination		Displays some knowledge of the indication for the examination		Displays ample knowledge of the indication for the examination
2. Applied knowledge of ultrasound equipment	1	2	3	4	5
Familiarity with the equipment and its functions, i.e. selecting probe, using buttons and application of gel.	Unable to operate equipment		Operates the equipment with some experience		Familiar with operating the equipment
3. Image optimization	1	2	3	4	5

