# 1. Overview of analysis

This document contains the statistical analysis plan for "Can a tailored quality assurance program help general practitioners maintain POCUS scanning competence?: A cohort study from Denmark". The study protocol (ClinicalTrials.gov ID NCT05625646) specified the intended analyses *prior to collection of the primary outcome*. This document elaborates on these intended analyses to be performed in the main study paper.

This study is a follow-up of a prior study (ClinicalTrials.gov ID NCT05274581) in which 18 general practitioners completed a tailored ultrasound educational program and had their ultrasound scanning competences assessed immediately after the program and at follow-up after three months. The three-month follow-up in the previous study is baseline for the present study.

Hence, data for the present study were gathered between September 7th 2022 and January 22nd 2024. Scanning competence scores were collected at baseline (September 7th and November 3rd 2022) and after 14 months (November 30th 2023 and January 22nd 2024). Quarterly quizzes were collected in: December 2022/January 2023(Quiz 1), March/April 2023(Quiz 2), August/September 2023(Quiz 3) and October/November 2023(Quiz 4). Remuneration fess for performed ultrasound scans were collected between November 2022 and November 2023. Background characteristic on participating general practitioners were collected on March 3rd 2022 when participants enrolled in the previous study and updated for the present study.

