**(S5):** For GPs, participating in a POCUS quality assurance program, the absolute number and proportion of GPs, who complete the online quiz at months 3, 6, 9 and 12 will be reported.

**(S6):** The results of the online quizzes at months 3, 6, 9 and 12 after baseline will be summarized and reported as tests scores for GPs, participating in a POCUS quality assurance program will be reported.

**(S7)**: For GPs, participating in a POCUS quality assurance program, we will graphically illustrate the relationship between total number of performed POCUS examinations for each of the ten scanning modalities included in the curriculum and OSAUS sum score at follow-up.

**(S8):** For GPs, participating in a POCUS quality assurance program, we will graphically illustrate the relationship between the number of completes quizzes in the quality assurance program and OSAUS sum score at follow-up.

**(S9):** For GPs, participating in a POCUS quality assurance program, we will graphically illustrate the relationship between the test score in the quizzes in the quality assurance program and OSAUS sum score at follow-up.

**(S10):** For GPs, participating in a POCUS quality assurance program, we will graphically illustrate the relationship between the OSAUS sum score at baseline and OSAUS sum score at follow-up.

**(S11):** the evaluation made by GPs, participating in a POCUS quality assurance program, will include:

- The absolute number and proportion of participants, who think the online quizzes helped them maintain scanning skills over the past year.

- The absolute number and proportion of participants, who think the online quizzes helped maintain focus on ultrasound over the past year.

- The absolute number and proportion of participants, who think the online quizzes developed their scanning skills over the past year.

- The absolute number and proportion of participants, who think the online quizzes were manageable in terms of time.

- The absolute number and proportion of participants, who think the online quizzes were manageable in terms of content.

- The absolute number and proportion of participants, who were overall satisfied with the online quizzes.

- The absolute number and proportion of participants, who think the OSAUS assessments have helped them maintain scanning skills over the past year?

- The absolute number and proportion of participants, who think the OSAUS assessments have developed their scanning skills over the past year.

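### The aim is causal, but one group without a comparator cannot credit maintained competence to the quizzes; a scan fee, outreach and baseline feedback add rival explanations

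*Protocol*

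**What the plan says.** **Aim and programme.** Protocol section 7 sets out to learn whether the programme "can lead to maintained scanning competence 12 months after baseline", and the title asks whether it can help. Section 11a is specific about content: "The program consists of an online quiz using a multiple choice questionnaire (MCQ) design". Quizzes are due at months 3, 6, 9 and 12, with feedback on the answers.

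**Design.** The study is labelled a cohort study. Allocation is marked not applicable (protocol 16a to 16c), and SAP section 4 describes one group. P1 summarises the follow-up score. P2 compares each GP's follow-up score with that GP's own baseline score.

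**Other exposures.**
- *Fee.* Protocol section 9: "There is no fee for performing POCUS in primary care", but "during this study participating GPs will have a fee for performing POCUS examinations". SAP section 1 says that fee records "were collected between November 2022 and November 2023".
- *Outreach.* Under protocol 11c a team member monitors scanning activity as well as quiz responses and will "reach out to participants, who fail be active or fail to complete the quizzes". SAP section 3 reports that this was done.
- *Assessor feedback.* Under protocol 18, after each OSAUS assessment "the participant will receive feedback on the level of performance and educational advice". The same section says that baseline and follow-up are carried out alike.

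S11 in SAP 5.2 counts GPs "who think the OSAUS assessments have helped them maintain scanning skills over the past year", so the SAP itself allows that being assessed may help to preserve skill.

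**The concern.** A statement that a programme leads to maintained competence compares what happened with what would have happened without it. This study observes only the first. The loss of skill to be expected over the interval without quizzes is not known from the documents; protocol section 6 says that it is unknown whether competence from the course can be kept up over time.

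The other exposures matter because they bear on the protocol's own explanation of skill loss. Section 6 lists infrequent scanning and lack of supervision among the obstacles. A fee and contact about low scanning activity bear on the first, and individual expert feedback bears on the second.

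At stake is the conclusion. If most GPs hold their score, readers could adopt quizzes alone on evidence that does not test quizzes alone.

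**Working it through.** **1. The plan's own figure.** 18 × 0.80 = 14.4, rounded up to 15 (15/18 = 83.3%), and 15 × 10 modalities = 150 OSAUS forms. Both reproduce. The documents give no power calculation, effect size, SD of change or margin.

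**2. Which exposures can influence P1 and P2?**

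| Exposure | In the 11a definition? | Who receives it | Can it affect P1/P2? |
|---|---|---|---|
| Quizzes with answer feedback | Yes | All are sent them | Yes |
| Scan fee | No (section 9 only) | Participating GPs | Possibly, through scan volume |
| Contact about missed quizzes | No (11c, adherence) | Those who fall short | Yes, but may count as delivery |
| Contact about low scanning | No (11c) | Those who fall short | Possibly, through scan volume |
| Feedback at baseline assessment | No (section 18) | Those assessed | Yes, it precedes the interval |
| Feedback at follow-up assessment | No (section 18) | Those assessed | No, it follows scoring |

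**3. Does any planned analysis separate the quizzes from the rest?** Protocol 20b leaves sub-analyses of the educational elements to the SAP, and the SAP defines none. S7 to S9 are linear regressions in protocol section 12 and graphs in SAP 5.2. Additional POCUS education is declared (11d) but enters no analysis. So none does.

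**4. Illustration of what P2 can show.** Assumptions: n = 15; within-GP change is normal; δ is the net mean change divided by the SD of change; ties are ignored. The quiz effect is set to zero, so δ is everything else (fee, contact, earlier feedback) minus natural decay.

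- Expected P2 = Φ(δ).
- The chance of at least 10 of 15 maintained is the upper binomial tail with probability Φ(δ).
- The chance of a significant rise (paired t-test, two-sided 0.05, 14 df) is the upper tail of a noncentral t with noncentrality δ√15. For δ = 0.5 this is 0.5 × 3.873 = 1.94.

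| δ | Expected P2 | P(at least 10 of 15) | P(significant rise) |
|---|---|---|---|
| −0.5 | 31% | 0.005 | 0.000 |
| −0.25 | 40% | 0.035 | 0.002 |
| 0 | 50% | 0.15 | 0.025 |
| 0.25 | 60% | 0.40 | 0.15 |
| 0.5 | 69% | 0.70 | 0.44 |
| 1.0 | 84% | 0.98 | 0.95 |

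P2 depends only on the net change. The ambiguity therefore runs both ways: decay of 1.0 SD with a quiz benefit of 0.5 SD also gives δ = −0.5 and an expected P2 of 31%, although the quizzes worked.

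**5. Precision.** Even the descriptive result will be loose. An observed 12/15 (80%) has an exact 95% interval of 52% to 96%. The 95% half-width for the mean change is 2.145/√15 = 0.55 SD.

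**The case against.** The strongest reply is that the study claims little. It is openly a cohort study, most outcomes are already phrased for GPs taking part in the programme, and no between-group effect is planned. That stands, and it is why the correction is small. The title and the aim still go further than the outcomes do.

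Several narrower objections also stand:

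- *The co-exposures are not the root cause.* Without fee, outreach and feedback, attribution would still fail, because there is one group. They add named rivals to a problem that the missing comparator already creates.
- *Outreach is declared as an adherence measure.* Contact about a missed quiz can fairly count as delivering the programme. Contact about low scanning acts on practice volume and is harder to place there.
- *Baseline feedback belongs to the previous study.* SAP section 1 makes that study's three-month follow-up the baseline here, with assessments dated 7 September and 3 November 2022; expected first enrolment was 15 November 2022. It is prior exposure, but it still precedes the change that P2 measures.
- *The fee may be mainly a recording device.* The fee codes are how S4 is measured. For S7, no difference in fee between GPs is described, so the fee does not obviously confound the relation between volume and score within the cohort. It bears on generalisability.
- *The wider package is hinted at.* Section 11a calls the quizzes one part of the intervention, but defines no other part.

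**Conclusion.** The point holds as one about what may be concluded. The aim and title are causal, the programme is defined as quizzes with feedback, and a single-group before-after cohort cannot attribute maintained competence to them. No planned estimate or analysis changes. The figures above rest on assumed values of δ; they show that a favourable P2 is compatible with no quiz effect, not that this is likely.

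Stronger readings are tempting but not supported:

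- A reader might infer that all 15 GPs receive every co-exposure. Outreach goes only to those who fall short, and 15 is an expected number.
- A reader might infer that the study pays for each scan and that the S4 and S7 counts are driven by payment. The documents state neither payer nor amount, and give no evidence that the fee changed behaviour.
- A reader might infer that the quizzes' share of the effect could lie anywhere from none to all. That presumes a total effect to divide. Without a reference for decay there is none, and the components need not be positive or additive.

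**What to change.** SAP section 1 reports data collection as complete, so the change belongs in the SAP overview and the study report.

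1. State the aim and conclusion descriptively, for example: *whether competence is maintained among GPs taking part in the programme, with a scan fee, activity outreach and prior assessor feedback also present.*
2. State that no effect is attributed to the quizzes, because there is no comparator.
3. Note that the S4 and S7 scan counts were recorded while a fee applied, which may limit generalisability to usual practice.
4. Report the number of outreach contacts per GP, if they were logged, separating contact about quizzes from contact about scanning where the log allows.

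The cost is a few sentences, one count and a narrower headline claim. No new data or design is required. A causal claim about the quizzes would need a different study, with a comparison group that has the same fee, contact and assessor feedback but no quizzes.

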
Secondary outcome 11 (S11): For GPs, participating in a POCUS quality assurance program, their evaluation of the program after 12 months..

3 Protocol version

Version 5 November 14th 2022

4 Funding

This study will be conducted as independent research at Center for General Practice at Aalborg University and is financially supported by The Novo Nordisk Foundation (grant number 0061821) and The General Practice Foundation in Denmark (grant number A3495).

5 Roles and responsibilities

5a Names, affiliations, and roles of protocol contributors

[name] (SKA) will be the principal investigator.

SKA, [name] (CAA) and [name] (MBJ) will oversee the choice of and collection of outcome measures.

CAA, SKA and MBJ wrote the first draft of the protocol.

[name] (SLC) will assist in statistical guidance. [name] (AR) will draft the statistical analysis plan.

CAA will handle participant correspondence. AR will handle the data cleansing and do the data analysis.

[name] (OG), MBJ, [name] (LP), [name] (CS) and SKA will perform the OSAUS evaluations of scanning competence at 12 months.

CAA, MBJ, SLC, OG, LP, CS and SKA are all expected to make valuable scientific additions to the draft and will be co-authors on subsequent manuscripts based on these data.

The definition of author is defined on ICMJE's four criteria¹:

Substantial contributions to the conception or design of the work; or the acquisition, analysis, or interpretation of data for the work; AND

Drafting the work or revising it critically for important intellectual content; AND

Final approval of the version to be published; AND

Agreement to be accountable for all aspects of the work in ensuring that questions related to the accuracy or integrity of any part of the work are appropriately investigated and resolved.

The expected author list is: [name], [name], [name], [name], [name], [name], [name], [name].

5b Name and contact information for the trial sponsor

Trial sponsor: Center for General Practice at Aalborg University (CAM AAU)

Contact name: [name]

Address: Center for General Practice in Aalborg, [name]

E-mail: [contact]

5c Role of study sponsor and funders

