The GPs are asked to declare any additional POCUS course activity or education during the study.

12 Outcome measures

Background characteristics of participating GPs

At baseline the following participant characteristics will be collected: Age (years), gender (M, F, other), previous use of ultrasound (number of months with regular use), previous ultrasound courses of minimum 1 day duration (yes/no), scanner type (low range, mid range, high end), type of practice (collaboration, partnership, solo), location of practice (urban, rural, mixed), number of patients assigned to the practice, and number of GPs working in the practice.

In addition, the results from the OSAUS assessment of scanning competences conducted on all participants in September or October 2022 will be included.

The OSAUS assessment tool has been developed and validated as a generic tool for assessing scanning competence¹⁴. The OSAUS scale consists of seven items: 'indication for the examination', 'applied knowledge of ultrasound equipment', 'image optimization', 'systematic examination', 'interpretation of images', 'documentation of the examination' and 'medical decision-making' and each item is rated using a five-point Likert-scale with descriptions of performance ranging from very poor (score = 1) to excellent (score = 5). All items are weighted equally, as high inter-item correlation have been found previously¹⁵. Hence, for each scanning modality a total score from 7 to 35 points may be achieved.

The OSAUS ultrasound competence assessment tool have been developed as a generic tool to assess ultrasound competence across medical specialities. The assessment tool was developed through a Delphi study¹⁴ and it has been used to assess clinicians' ability to transfer learning from an ultrasonography course into diagnostic performance on patients. Furthermore, the tool has been found valid and reliable to distinguish between novice POCUS users and experts¹⁶.

For the primary outcome(P1) and secondary outcomes (S1-S2) we will use the Objective Structured Assessment of Ultrasound Skills (OSAUS) score scored after 12 months. For the primary outcome (P2) we will use the OSAUS score at baseline and at 12 months.

Primary outcomes:

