(P1): The summarized OSAUS score after 12 months for all ten modalities will be calculated as percentage of maximum score. To summarize normal and non-normal distributed data similarly mean(SD) as well as median(IQR) will be presented together with minimum and maximum scores.

Primary outcome 2 (P2):

The summarized OSAUS score at baseline and at 12 months for each participating GP will be compared and the proportion of GPs, with an OSAUS score at 12 months larger than or equal to the ultrasound competence score at baseline, will be reported.

Secondary outcomes

(S1): For GPs, participating in a POCUS quality assurance program, the OSAUS scores and the item scores after 12 months, for each of the ten scanning modalities included in the curriculum will be calculated and presented as median, IQR, minimum and maximum score.

(S2): We calculate the proportion of GPs, who achieve a minimum OSAUS score of three for all seven domains for each of the ten scanning modalities after 12 months. As variation in scores can occur between the four expert assessors. We will normalize the scores by multiplying a given accessors score with (0.2 x sum of scores of all five accessors/the given accessors mean score) prior to calculating the proportion of successful GPs.

For the secondary outcome S3, we will use the GPs assessment of their own scanning competence. The GPs will declare to which degree they have POCUS scanning competence within a specific scanning modality to perform the scan un-supervised in general practice (To a very high degree, to a high degree, to some degree, to a lesser degree, not at all, unsure).

(S3): We calculate the proportion of GPs, who rate themselves as competent to perform POCUS un-supervised in general practice, after the educational period (three months after baseline), within each of the ten scanning modalities.

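### The protocol's S2 rescales integer item scores by assessor before a cut of 3 without rounding, which almost only removes passes, and the SAP does not say whether an adjusted or a raw version is S2

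*Protocol*

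**What the plan says.** **Scale.** Protocol section 12 describes OSAUS as seven items, and "each item is rated using a five-point Likert-scale with descriptions of performance ranging from very poor" (1) to excellent (5). Item scores are therefore integers.

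**S2 in the protocol.** Section 12 counts a GP as successful in a modality if all seven items score at least 3. Scores are first normalised by "multiplying a given accessors score with (0.2 x sum of scores of all five accessors/the given accessors mean score"), and this is done "prior to calculating the proportion of successful GPs". No rounding of the rescaled scores is mentioned.

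**Number of assessors.** The sentence that introduces the normalisation reads "As variation in scores can occur between the four expert assessors", yet the formula speaks of five. Section 5a lists five people who "will perform the OSAUS evaluations of scanning competence at 12 months". Section 10 names the same five ("The competence assessment (OSAUS score) will be delivered by a team of POCUS experts").

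**S2 in the SAP.** Section 5.2 restates S2 as an item score of at least 3 on all seven items and names no normalisation. Section 1 describes the SAP's relation to the protocol in these words: "This document elaborates on these intended analyses to be performed in the main study paper".

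**SAP section 9.** Results are adjusted so that the experts share one average score. OSAUS scores are tabulated twice: as raw complete cases, and as a version with both imputation and expert adjustment, which the SAP calls statistically optimal. S2 is not mentioned there. The form of the adjustment (additive or multiplicative) and any rounding are not given either.

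**The concern.** A cut of 3 on an integer scale leaves no slack: a raw 3 sits exactly on the boundary. Any multiplier below 1, however close to 1, moves it to the failing side, whereas a raw 2 needs a multiplier of 1.5 to cross upward. A step meant to even out severity between assessors thus acts mainly as a higher pass mark for GPs seen by assessors with above-average means.

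An assessor's mean also reflects how able the GPs were whom that assessor happened to see, so the pass mark moves even if all assessors are equally severe. Only one assessor is present at each assessment, so two GPs with identical ratings can differ on S2 because of who scored them.

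S2 is the only expert-rated outcome that says how many GPs reach a competence standard (S3 is self-rated). If raw and adjusted values differ materially and no rule names one of them as S2, the headline value can be chosen after both have been seen.

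**Working it through.** **1. The weight.** 1/5 = 0.2, so the stated weight fits five assessors; four would need 1/4 = 0.25. If only four were summed with weight 0.2, every factor would be multiplied by 4 × 0.2 = 0.8, and even an exactly average assessor would apply a cut of 4.

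**2. The reading of the formula.** Taken literally, the numerator is a sum of scores and the denominator a mean. With 150 forms (protocol section 14), seven items and an assumed mean item score of 4, the factor would be 0.2 × (150 × 7 × 4) / 4 = 210, and every score would pass. The only reading centred near 1 is

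f = (mean of the five assessor means) / (assessor's own mean).

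The rest uses that reading; the wording itself needs correcting.

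**3. Effective cut without rounding.** This needs no score distribution.
- Raw 3 passes if 3f ≥ 3, so f ≥ 1: own mean at or below average.
- Raw 4 passes if 4f ≥ 3, so f ≥ 0.75: own mean at most 4/3 of average.
- Raw 2 passes if 2f ≥ 3, so f ≥ 1.5: own mean at most 2/3 of average.

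Unless all five means tie, at least one assessor lies above average and applies a cut of 4 or more. An own mean of 4.01 against an average of 4.00 is enough: 3 × 4.00/4.01 = 2.993. An additive adjustment does the same: with an own mean of 4.1, raw 3 becomes 3 − (4.1 − 4.0) = 2.90.

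**4. Worked example.** Assumed assessor means 3.6, 3.7, 3.8, 3.9, 4.0; average 3.8.
- Raw 3 becomes 3 × 3.8/3.6 = 3.17, then 3.08, 3.00, 2.92 and 2.85.
- The most favourable raw 2: 2 × 3.8/3.6 = 2.11, a fail.
- The least favourable raw 4: 4 × 3.8/4.0 = 3.80, a pass.

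Two of five assessors apply a cut of 4 and three a cut of 3. If each scores three GPs, 6 of 15 GPs face the higher cut and nobody faces a lower one.

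**5. Effective cut with rounding to the nearest integer.** Raw 3 passes if 3f ≥ 2.5, so f ≥ 0.833 (own mean up to 20% above average). Raw 2 passes if 2f ≥ 2.5, so f ≥ 1.25. The shift largely disappears.

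**6. Size by simulation.** The documents give no score distribution or assessor allocation, so everything here is assumed: 15 GPs and 5 assessors; mean item score 3.6, 3.9, 4.2 or 4.5; SDs for GP / GP-by-modality / residual of 0.2/0.2/0.4, 0.3/0.3/0.5 or 0.4/0.4/0.7; assessor severity SD 0, 0.2 or 0.4; one assessor per GP or rotating by modality. That makes 4 × 3 × 3 × 2 = 72 scenarios. Latent scores are rounded and clipped to 1–5.

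These SDs imply latent within-modality inter-item correlations of 0.08/0.24 = 0.33, 0.18/0.43 = 0.42 and 0.32/0.81 = 0.40. Protocol section 12 reports that inter-item correlation has been found to be high, so the scenarios were repeated at 0.7, 0.8 and 0.9 (an assumed range for high) with total variance unchanged.

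Fall in S2, raw minus unrounded adjusted, percentage points per modality:

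| Inter-item correlation | Median | Maximum | Scenarios with a fall of at least 3 of 15 GPs |
|---|---|---|---|
| 0.33–0.42 | 22 | 39 | 41 of 72 |
| 0.7 | 15.9 | 31.1 | 26 of 72 |
| 0.8 | 13.3 | 29.1 | 18 of 72 |
| 0.9 | 11.1 | 25.2 | 12 of 72 |

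The maxima at high correlation equal 0.25 × 15 to 0.31 × 15, about 4 to 5 GPs. The unrounded adjusted S2 was nearer than the raw S2 to the rate with no severity differences in 0 of 72 scenarios, at low and at high correlation. At 0.33–0.42, rounding before the cut put S2 only 0 to 1.6 points above raw.

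**The case against.** The strongest reply is that the SAP has already dealt with this. Its section 5.2 defines S2 on item scores with no normalisation, which points to raw scores, and section 9 commits to showing raw results beside adjusted ones, so a raw version cannot quietly disappear. That stands, and it limits the concern. A reader might infer that the SAP will apply the protocol's multiplier to S2, or that the reported S2 must be too low. The documents do not support either: section 9 never mentions S2, a proportion, a multiplicative form or an order of steps. What remains is that the SAP presents itself as elaborating the protocol and does not say that it withdraws the protocol's rule. Section 9 also leaves open whether its adjustment reaches the cut and which version is S2.

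A second reply concerns size. The larger simulated falls rest on moderate inter-item correlation, while the protocol itself reports high correlation, and a rule requiring all seven items is sensitive to this. That stands too. The highly correlated scenarios fit the protocol better and give smaller falls; the direction is the same in all of them.

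A third reply is that raw scores give up the protocol's correction for severe assessors. That is a real cost, but the unrounded rule does not deliver the correction either.

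**Conclusion.** The protocol's S2 rule is wrong as written. With integer items, a cut of 3 and no rounding, the rescaling almost only removes passes and makes the pass mark depend on the assessor. That follows from arithmetic once the factor is read as centred near 1. The SAP's wording of S2 points to raw scores but does not settle the matter.

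The size rests on assumed scenarios: a median fall of about 11 to 16 points (maximum 25 to 31, about 4 to 5 of 15 GPs) at inter-item correlations of 0.7 to 0.9, and about 22 points (maximum 39) at 0.33 to 0.42. These show how far two versions of S2 could lie apart; they do not estimate an error in any reported result.

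A reader might extend the point to the study's main conclusions. The documents do not support that: the protocol attaches this rescale-then-cut rule to S2 alone, S2 is descriptive and secondary, and P1, P2 and the sample size are not affected. It should be fixed because the remedy is cheap.

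**What to change.** Add a dated note to SAP section 5.2, disclosed as a change from the protocol and as made after data collection. SAP section 1 says that "data for the present study were gathered between September" 2022 and January 2024. Suggested text:

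*The main S2 result is computed on the raw integer item ratings; neither the protocol normalisation nor the section 9 expert adjustment is applied before the cut of 3.*

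The same note should state that:
- any adjusted S2 is a labelled sensitivity result, with factor equal to the mean of the five assessor means divided by the assessor's own mean, and adjusted scores rounded to the nearest integer before the cut;
- the main S2 uses complete-case items, with imputed items only in the sensitivity version;
- the count of four assessors in protocol section 12 should read five.

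The protocol text of 2022 stays as it is. The cost is a short note and no new data. The downside is that the main S2 is not corrected for assessor severity: in the assumed scenarios it lies up to about 8 to 9 points below the rate without severity differences at a severity SD of 0.4, less if items are highly correlated. At inter-item correlations of 0.33–0.42, adjusting and then rounding would recover at most 1.6 points of that.
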